5.1 Cancellation Guidelines

If a participant does not receive an injection of the radiotracer, the participant may be canceled. Reasons for cancellation must be documented. Note: A patient may only be canceled if no investigational drug is administered.

5.2 Withdrawal of Consent

Participants may voluntarily withdraw consent at any time or for any reason during the study without effect on their further management/treatment.

5.3 Withdrawal of a Participant by the Investigator

Reasons for withdrawal might include:

- Participants may be withdrawn from the study, prior to any imaging studies, by the investigator if deemed medically necessary.
- Inter-current illness, abnormal laboratory values, and/or adverse events that precludes further study participation.
- Significant protocol violation or noncompliance.
- The study is terminated.

Reason for discontinuation from the study should be adequately documented. Data will be collected for all withdrawn subjects up until the time of discontinuation.

5.4 Early Stopping Rules

The safety and tolerability will be assessed on an ongoing basis during the course of the study. The study will be halted and safety and dosing will be further evaluated if any single patient experiences a grade 3-5 toxicity that is believed to be related to radiotracer administration

6. PHARMACEUTICAL AND/OR IMAGING AGENT INFORMATION

6.1 ^{111}In -XYIMSR-01 Investigational Product:

6.1.1 Drug Substance

Common Name: ^{111}In -XYIMSR-01

Unit Dose: 10.5 ± 1 mCi of ^{111}In -XYIMSR-01 followed by SPECT/CT imaging

Route of administration: Intravenous catheter placed in an antecubital vein or an equivalent venous access

6.1.2 ^{111}In -XYIMSR-01 Manufacturer

The radiotracer will be manufactured at the Center for Translational Molecular Imaging located

at [name].

7. ANALYSIS PLAN AND STATISTICAL CONSIDERATIONS

7.1 Primary Objective

The primary objective of this study is to evaluate the safety, tolerability, and feasibility of SPECT/CT imaging with ^{111}In -XYIMSR-01. All adverse events (AEs) will be graded according to the Common Terminology Criteria for Adverse Events (CTCAE) version 5.0. The principal investigator or designee will determine if an observed adverse event is attributable to radiotracer administration. Based on our experience with similarly dosed radiotracers, we do not expect any grade 3-5 radiotracer-related adverse events. If the observed rate is indeed 0%, then a sample size of 10 patients will allow for 90% confidence that the actual toxicity of the radiotracer is in the range of 0% to 25%.

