1. BACKGROUND

1.1 Study Disease(s)

Renal cell carcinoma (RCC) & Carbonic Anhydrase IX (CAIX): Renal cell carcinoma (RCC) is the most common neoplasm of the kidney [1], with an estimated 60,000 patients diagnosed annually in the United States [2]. Among cases of RCC, the clear cell subtype (ccRCC) is the most prevalent, accounting for up to 70% of RCCs [3–5]. Common to ccRCC is loss of the Von Hippel-Lindau (*VHL*) tumor suppressor gene [6]. Loss of *VHL* in turn leads to over-expression of carbonic anhydrase IX (CAIX) [7], a membrane-associated enzyme responsible for catalyzing the reversible hydration of carbon dioxide to a bicarbonate anion and a proton [8, 9]. Overexpression of CAIX is known to be presented in approximately 95% of ccRCC tumor specimens [10–12], making it a useful biomarker for this disease.

CAIX has limited expression in normal tissues with the exception of the gastrointestinal tract, gallbladder and pancreatic ducts [8, 9, 13–15]. Feasibility for the non-invasive detection of ccRCC based on CAIX expression has been proved with the radiolabeled antibody G250 [16] and its potential clinical applications has been reviewed previously [17]. However, antibodies as molecular imaging agents suffer from pharmacokinetic limitations, including slow blood and non-target tissue clearance (normally 2–5 days or longer) and non-specific organ uptake. Low molecular weight agents demonstrate faster pharmacokinetics and higher specific signal within clinically convenient times after administration. Low molecular weight agents can also be synthesized in radiolabeled form more easily, and may offer a shorter path to regulatory approval [18].

Targeting CAIX with small molecule inhibitors has proved challenging in part because there exists fifteen human isoforms of carbonic anhydrase. These isoforms share common structural features, including a zinc-containing catalytic site, a central twisted β -sheet surrounded by helical connections, and additional β -strands. The isoforms, however, vary widely in terms of intracellular location, expression levels, and tissue distribution [8, 9]. Significant effort has been expended on the development of sulfonamides and other low molecular weight CAIX ligands for nuclear imaging, but most reported agents have been fraught with low tumor uptake and significant off-target accumulation [19–24].

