2. OBJECTIVES

2.1 Primary Objectives:

The primary objective of this study is to evaluate the safety, tolerability, and feasibility of ^{111}In -XYIMSR-01 SPECT/CT in patients with metastatic ccRCC.

2.2 Secondary Objectives:

- To determine the biodistribution and radiation dosimetry of ^{111}In -XYIMSR-01.
- To characterize the pharmacokinetics of ^{111}In -XYIMSR-01.
- To assess the concordance of findings on ^{111}In -XYIMSR-01 SPECT/CT with conventional imaging.

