3. STUDY DESIGN AND SUBJECT POPULATION

3.1 Study design

The study is phase I, open label, single-arm study designed to evaluate the safety, tolerability, and feasibility of ^{111}In -XYIMSR-01 SPECT/CT in patients with metastatic ccRCC.

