7.2 Secondary Objectives

Biodistribution and Radiation Dosimetry: A secondary objective of this study is to determine the biodistribution and radiation dosimetry of ^{111}In -XYIMSR-01. To allow for this, SPECT/CT images will be acquired at 2-4, 24 ± 1 hour, and 48 ± 1 hour post-injection. For the first three patients a total of three fields of view will be acquired and for the remaining 7 patients two fields of view will be acquired. Each SPECT acquisition will be acquired over a 20-30 minute period. The first time point acquisition for each field of view will include a high resolution CT. All other time points will be acquired with a low-dose CT.

The acquired PECT/CT images will be used to perform the biodistribution and radiation dosimetry calculations. Time-activity curves (TACs) demonstrating radiotracer activity as a function of time post injection (minutes) will be drawn for the whole body and the following organs: brain, breast, gallbladder, stomach, pancreas, heart wall, lung, liver, bladder, muscle, pancreas, red marrow, spleen, adrenals, upper large intestine, lower large intestine, small intestine, thymus, thyroid, testes and ovaries. Individual organ residence times will be calculated by fitting an exponential function to the TAC data and analytically integrating the fitted functions from zero to infinity. Organ specific mean radiation-absorbed dose estimates for ^{111}In -XYIMSR-01 will be calculated from the individual organ residence times. Reference organ mass values will be adjusted based on actual organ masses. The OLINDA software package will be used to determine the absorbed dose [28].

Characterization of Pharmacokinetics: The pharmacokinetic profile of ^{111}In -XYIMSR-01 will be determined as a secondary endpoint of the study. ~5 mL of blood will be collected in heparinized tubes at pre-dose, 5 ± 2 minutes, 10 ± 2 minutes, 20 ± 5 minutes, 30 ± 5 minutes, 1 ± 0.25 hour, 1.5 ± 0.25 hour, and 24 hours ± 1 hour, post-injection to estimate elimination half-life. The collected blood will be evaluated for total radioractivity, the ratio of free versus protein-bound radiotracer, and measurement of the relative percentage of radiotracer and its metabolites.

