7.3 Sample Size/Accrual Rate

We plan to enroll 10 patients diagnosed with Metastatic Clear Cell Renal Cell Carcinoma. We do not expect any severe radiotracer-related adverse events based on our experience with similar types of radiotracers. We will pause the accrual and re-evaluate safety if one or more patients experience grade 3-5 toxicity that is believed to be related to radiotracer administration.

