9. STUDY OVERSIGHT AND DATA REPORTING / REGULATORY REQUIREMENTS

9.1 Data and Safety Monitoring Plan

Data and Safety Monitoring:

This is a DSMP Medium Risk study under the SKCCC Data and Safety Monitoring Plan (02/21/2019). Data Monitoring of this protocol will occur annually. The protocol will be monitored internally at SKCCC by the Principal Investigator and externally by the SKCCC CRO in accordance with SKCCC guidelines. Trial monitoring and reporting will be done through the Safety Monitoring Committee (SMC) at SKCCC.

Additionally, scheduled meetings will take place monthly and will include the protocol principal investigator, research team, and, when appropriate, the collaborators, subinvestigators, and biostatistician involved with the conduct of the protocol.

The PI, [name], is responsible for monitoring and oversight of problem/events. Scheduled meetings will take place monthly and will include the protocol principal investigator, data manager, and, when appropriate, the collaborators, sub-investigators, and biostatistician involved with the conduct of the protocol.

During these meetings, the investigators will discuss matters related to: safety of protocol participants, validity and integrity of the data, enrollment rate relative to expectation, characteristics of participants, adherence to protocol (potential or real protocol violations), data completeness, and progress of data for study objectives.

The PI is responsible for internally monitoring the study. Data must be reviewed to assure the validity of data, as well as, the safety of the subjects. The PI will also monitor the progress of the trial, review safety reports, and clinical trial endpoints and to confirm that the safety outcomes favor continuation of the study.

The PI, [name], will be the medical monitor for this study. The medical monitor will make an assessment regarding the safety of continuing or modifying the study.

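### Does feasibility, named in the primary objective without an endpoint or denominator, call for a change to the plan?

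*Combined protocol and SAP*

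**What the plan says.** All references are to the combined protocol and SAP.

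- Feasibility appears in three statements of purpose. Section 2.1 reads "The primary objective of this study is to evaluate the safety, tolerability, and feasibility of" the imaging procedure, section 3.1 reads "The study is phase I, open label, single-arm study designed to evaluate the safety, tolerability, and feasibility of" the same procedure, and section 7.1 repeats the aim as "evaluate the safety, tolerability, and feasibility of SPECT/CT imaging".
- After that sentence, section 7.1 covers CTCAE grading, attribution by the investigator, and the claim that no events in 10 patients gives 90% confidence in a toxicity rate of 0% to 25%.
- Section 7.3 gives the size: "We plan to enroll 10 patients diagnosed with Metastatic Clear Cell Renal Cell Carcinoma". Its heading mentions an accrual rate, but none is given.
- Section 5.1 says: "If a participant does not receive an injection of the radiotracer, the participant may be canceled". It requires the reason to be recorded and allows cancellation only when no study drug was given. It is silent on counting and replacement.
- Sections 4 and 7.2 schedule three imaging sessions per patient, with three fields of view for the first three patients, while "for the remaining 7 patients two fields of view will be acquired".
- Section 9.1 lists "enrollment rate relative to expectation" and data completeness among the topics for monthly meetings.

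**The concern.** A component of the primary objective normally comes with something to measure, and this one does not. The word could also be read in two ways. Section 1.1 uses it for disease detection ("Feasibility for the non-invasive detection of ccRCC based on CAIX expression has been proved with the radiolabeled antibody G250"), but lesion detection in this study is a secondary objective under section 7.2. That leaves the operational reading: could patients be injected and imaged as planned?

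On that reading the denominator matters. Someone who enrols but never reaches injection may be a feasibility failure, and section 5.1 allows exactly that person to be cancelled. If the measure were chosen after the data were in, a report could give 100% of injected patients and leave out those who dropped away earlier. What is at stake is how one descriptive proportion is reported, not any safety finding.

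**Working it through.** **1. The plan's own figure.** Inputs: n = 10, no events, 90% confidence (section 7.1). The exact two-sided 90% upper limit for 0/n is 1 − 0.05^(1/n). With n = 10 it is 1 − 0.05^(0.1) = 25.9%; the Agresti-Coull limit is 24.9%. The stated 25% is a fair rounding. The sample size therefore rests on toxicity alone and presumes ten injected patients.

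**2. Toxicity if cancelled participants used up places.** The same formula gives 28.3% for n = 9, 31.2% for n = 8 and 34.8% for n = 7. The steps are 2.4, 2.9 and 3.6 points, 8.9 in all. This would arise only without replacement. The split of imaging into the first three and the remaining seven patients (3 + 7 = 10) points towards ten imaged patients, although section 4 calls the first three enrolled in the same sentence, so the point is not settled.

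**3. Feasibility under each denominator.** The plan gives no cancellation rate, so 1, 2 and 3 cancellations are assumptions. Everyone injected is assumed to complete. Brackets hold exact two-sided 90% intervals.

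| Cancelled | Of enrolled, not replaced | Of injected, not replaced | Of enrolled, replaced until 10 injected |
|---|---|---|---|
| 0 | 10/10 = 100% (74.1–100) | 10/10 = 100% (74.1–100) | 10/10 = 100% (74.1–100) |
| 1 | 9/10 = 90% (60.6–99.5) | 9/9 = 100% (71.7–100) | 10/11 = 90.9% (63.6–99.5) |
| 2 | 8/10 = 80% (49.3–96.3) | 8/8 = 100% (68.8–100) | 10/12 = 83.3% (56.2–97.0) |
| 3 | 7/10 = 70% (39.3–91.3) | 7/7 = 100% (65.2–100) | 10/13 = 76.9% (50.5–93.4) |

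With replacement, the proportion of injected patients is 10/10 in every row. The choice of denominator moves the estimate by 10 to 30 points without replacement and by 9.1 to 23.1 points with it.

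**4. A mixed case.** Suppose one of 10 enrolled is cancelled and one injected patient misses only the 48-hour scan. All three sessions are completed by 8/10 = 80% of enrolled or 8/9 = 88.9% of injected. At least one scan is completed by 9/9 = 100% of injected. Of 10 × 3 = 30 planned sessions, 30 − 3 − 1 = 26 are done, or 86.7%.

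**5. Can the missing figures be rebuilt from what the plan already collects?** Enrolment and injection are known for each participant. Section 5.1 requires the reason for each cancellation and closes that route after dosing, so a failed or missed scan after injection cannot be removed by cancelling the patient. Section 5.3 keeps data on withdrawn participants up to discontinuation. Scans follow timed windows (section 4). Every count in steps 3 and 4 can be produced from these records.

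**6. Does any decision use feasibility?** The halt in sections 5.4 and 8.1 and the pause in section 7.3 depend on related grade 3–5 toxicity. No rule refers to feasibility.

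**The case for a change.** The strongest case for a change is that feasibility is one of three named parts of the primary objective and the only one with no planned output that can be recognised as its own, since tolerability can at least be read from the adverse events. The authors say so when they intend a descriptive summary, as in the lesion comparison of section 7.2, and feasibility has no such sentence. The mixed case gives four defensible figures between 80% and 100%, and a short definition would cost little.

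Part of this stands. The documents do not define the measure, and they do not settle whether ten means enrolled or injected.

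The rest carries less weight. The spread between figures is a reporting choice that disappears once both denominators are shown, and ten patients can be listed individually. Neither denominator is plainly right: the stated aim concerns imaging with the tracer, and someone never given it says little directly about that, so injected patients are a natural base here as they are for toxicity. A stricter endpoint requiring evaluable images would not be free, because the plan has no evaluability criterion and schedules no such assessment. A success threshold would also mean little at this size: even 10/10 excludes only completion rates below 74.1%.

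**Conclusion.** No change is needed. The plan leaves feasibility undefined, but this is a missing detail and not an error: no figure, rule or analysis that it states is wrong. On the assumed 1 to 3 cancellations, completion reads 100% of injected against 90% to 70% of enrolled without replacement, or 90.9% to 76.9% with replacement. Nothing in the conduct of the study turns on which is quoted. The 0% to 25% toxicity statement holds for ten injected patients whatever definition of feasibility is used.

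This rests on two assumptions: that the report gives enrolled, injected and fully imaged counts together with the recorded cancellation reasons, and that feasibility is described and not tested. Both are ordinary practice for a ten-patient, single-arm phase I imaging study, and the data for them are already collected.

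### Is the 90% confidence range of 0% to 25% for zero events in 10 patients miscalculated?

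*Combined protocol and SAP*

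**What the plan says.** Section 7.1 (Primary Objective) first gives the expectation: "we do not expect any grade 3-5 radiotracer-related adverse events". It then makes a planning statement that is conditional on seeing no such event: "10 patients will allow for 90% confidence that the actual toxicity of the radiotracer is in the range of 0% to 25" percent. It gives no interval method, does not say whether the 90% is one-sided or two-sided, and does not describe the calculation as exact.

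Section 7.3 (Sample Size/Accrual Rate) gives the number again, "We plan to enroll 10 patients diagnosed with Metastatic Clear Cell Renal Cell Carcinoma", and repeats that no severe related events are expected. It adds no further precision figure.

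The rule that acts on safety is separate. Sections 5.4 and 8.1 halt the study, and Section 7.3 pauses accrual, once a single patient has a grade 3-5 toxicity attributed to the tracer.

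**The concern.** With zero events the lower limit is 0%, so a range from 0% to some value amounts to an upper confidence bound. Most statisticians would check such a bound with the exact binomial formula. For 0 of 10 that formula gives 20.6% (one-sided 90%) or 25.9% (two-sided 90%), and neither is 25%. Turned round, a bound of 25% carries 94.4% one-sided confidence rather than 90%. The stated confidence and the stated bound therefore seem not to belong together.

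If that were so, the only statistical support for 10 patients would be wrong, and readers would be misled about how high a rate of serious related toxicity remains compatible with a clean result.

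**Working it through.** **Inputs.** n = 10 (Sections 7.1 and 7.3). Observed events x = 0, confidence 90% and stated range 0% to 25% (Section 7.1).

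**1. Reproducing the plan's figure.** Two-sided 90% Agresti-Coull interval, z = 1.645, z² = 2.706:

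- adjusted size: 10 + 2.706 = 12.706
- adjusted proportion: (0 + 2.706/2) / 12.706 = 0.1065
- standard error: √(0.1065 × 0.8935 / 12.706) = 0.0865
- limits: 0.1065 ± 1.645 × 0.0865, that is −3.6% to 24.9%

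A negative lower limit is set to 0% as a matter of routine. The interval is 0% to 24.9%, which rounds to the stated 0% to 25%.

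**2. The exact binomial readings.**

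- One-sided 90% upper bound: 1 − 0.10^(1/10) = 20.6%.
- Two-sided 90% (Clopper-Pearson) upper limit: 1 − 0.05^(1/10) = 25.9%. This is also the one-sided 95% bound.
- One-sided confidence that the rate is at most 25%: 1 − 0.75^10 = 1 − 0.056 = 94.4%.
- The same with 5.6% counted in each tail: 1 − 2 × 0.056 = 88.7% (from the unrounded value 0.0563).

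**3. Setting each reading against the sentence.**

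| Reading | Result for 0 of 10 | Plan's 25% is |
|---|---|---|
| Two-sided 90%, Agresti-Coull | 24.9% | matched on rounding |
| One-sided 90%, exact | 20.6% | conservative |
| Two-sided 90%, Wilson | 21.3% | conservative |
| Two-sided 90%, Jeffreys | 17.1% | conservative |
| Two-sided 90%, Clopper-Pearson | 25.9% | too favourable by 0.9 points |

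**4. Effect on the sample size.** An exact two-sided 90% limit at or below 25% needs log(0.05)/log(0.75) = 10.4, so 11 patients, where the limit is 23.8%. An exact one-sided 90% bound at or below 25% needs log(0.10)/log(0.75) = 8.004, so strictly 9 patients; with 8 the bound is 25.01%. The planned 10 lies between the two answers, one patient away from each.

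**The case for a change.** The strongest case against the plan is that the figure cannot be traced. Agresti-Coull is one of several intervals, the plan does not name it, and a match found by trying methods does not prove that it was used. An unnamed method also leaves a choice open if the trial does not end at 0 of 10. With 0 of 9, the 90% upper limit is 22.6% (exact one-sided), 28.3% (exact two-sided) or 26.9% (Agresti-Coull). With 1 of 10 it is 33.7%, 39.4% or 36.4%. Either way the spread is about 6 points, and the choice could be made after the data are seen.

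The part that stands is that method and sidedness are not stated. That is a missing detail and does not make the number wrong. The two exact readings also depart from 25% in opposite directions, so the exact formula alone cannot show which way the sentence would be in error.

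The fear of a later choice carries little weight here. Section 7.1 does not commit the final report to this interval; it is a planning remark that applies if no event occurs. With about 10 patients the raw count will be plain, and any reader can put the preferred interval on it. If a related grade 3-5 event does occur, the plan's response is the halt or pause after one event, and no confidence limit enters that decision.

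**Conclusion.** The concern does not hold. The exact figures of 20.6%, 25.9% and 94.4% are correct, but they test the sentence against a method that the plan does not claim. A standard two-sided 90% interval reproduces 0% to 25% on rounding. On the one-sided exact reading the statement is true and cautious, because 94.4% confidence satisfies a claim of 90%. The single unfavourable reading, Clopper-Pearson two-sided, differs by 0.9 percentage points.

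Nothing in the plan turns on that gap. The documents set no toxicity threshold, test or go/no-go rule at 25%, and the halt or pause acts on a single related event.

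This conclusion rests on two assumptions: that the 90% may be read either as a two-sided level or as a minimum one-sided level, since the text excludes neither, and that the condition in the sentence, no events in 10 patients, is met.

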7.2 Secondary Objectives

Biodistribution and Radiation Dosimetry: A secondary objective of this study is to determine the biodistribution and radiation dosimetry of ^{111}In -XYIMSR-01. To allow for this, SPECT/CT images will be acquired at 2-4, 24 ± 1 hour, and 48 ± 1 hour post-injection. For the first three patients a total of three fields of view will be acquired and for the remaining 7 patients two fields of view will be acquired. Each SPECT acquisition will be acquired over a 20-30 minute period. The first time point acquisition for each field of view will include a high resolution CT. All other time points will be acquired with a low-dose CT.

The acquired PECT/CT images will be used to perform the biodistribution and radiation dosimetry calculations. Time-activity curves (TACs) demonstrating radiotracer activity as a function of time post injection (minutes) will be drawn for the whole body and the following organs: brain, breast, gallbladder, stomach, pancreas, heart wall, lung, liver, bladder, muscle, pancreas, red marrow, spleen, adrenals, upper large intestine, lower large intestine, small intestine, thymus, thyroid, testes and ovaries. Individual organ residence times will be calculated by fitting an exponential function to the TAC data and analytically integrating the fitted functions from zero to infinity. Organ specific mean radiation-absorbed dose estimates for ^{111}In -XYIMSR-01 will be calculated from the individual organ residence times. Reference organ mass values will be adjusted based on actual organ masses. The OLINDA software package will be used to determine the absorbed dose [28].

Characterization of Pharmacokinetics: The pharmacokinetic profile of ^{111}In -XYIMSR-01 will be determined as a secondary endpoint of the study. ~5 mL of blood will be collected in heparinized tubes at pre-dose, 5 ± 2 minutes, 10 ± 2 minutes, 20 ± 5 minutes, 30 ± 5 minutes, 1 ± 0.25 hour, 1.5 ± 0.25 hour, and 24 hours ± 1 hour, post-injection to estimate elimination half-life. The collected blood will be evaluated for total radioractivity, the ratio of free versus protein-bound radiotracer, and measurement of the relative percentage of radiotracer and its metabolites.

Comparison with Anatomical Imaging: As an initial assessment of the diagnostic performance of ^{111}In -XYIMSR-01 SPECT/CT, findings on this novel imaging test will be compared to those on conventional imaging (CT and/or MRI). Using descriptive statistics we plan to summarize the number of lesions that are detected with all imaging modalities, the number of lesions detected

with ^{111}In -XYIMSR-01 SPECT/CT but not with conventional imaging, and the number of lesions detected with conventional imaging but not by ^{111}In -XYIMSR-01 SPECT/CT.

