⁷ SPECT/CT will be acquired at 2-4, 24± 1 hour, and 48± 1 hour post-injection. For the first three enrolled patients, a total of three fields of view will be acquired and for the remaining 7 patients two fields of view will be acquired. Each SPECT acquisition will be acquired over a 20-30 minute period.

⁸ A safety phone call will also occur 7(±3) days post-dosing. Ongoing adverse events thought to be related to ¹¹¹In-XYIMSR-01 will be followed until resolution of the adverse event, until an alternate cause has been identified, the patient is lost to follow-up, the patient withdraws consent, or it has been determined that ¹¹¹In-XYIMSR-01 is not the cause of the adverse event.

⁹ In order to minimize the need for research-only in-person visits, telemedicine visits may be substituted for in-person research study visits or portions of research study visits where determined to be appropriate and where determined by the investigator not to increase the participants' risks. Prior to initiating telemedicine for study visits the study team will explain to the participant, what a telemedicine visit entails and confirm that the study participant is in agreement and able to proceed with this method. Telemedicine acknowledgement will be obtained in accordance with the Guidance for Use of Telemedicine in Research. In the event telemedicine is not deemed feasible, the study visit will proceed as an in-person visit. Telemedicine visits will be conducted using HIPAA compliant method approved by the Health System and within licensing restrictions.

¹⁰ Safety blood tests: comprehensive metabolic panel to monitor blood chemistries, including kidney and liver function, and blood cell count will be collected at the end of 48 hour SPECT/CT imaging.

¹¹ A 12-lead electrocardiogram will be conducted at the end of 48 hour SPECT/CT imaging.

Pharmacokinetics & Imaging Timepoints:

Procedure	Pre-dose	0 hour	5± 2min.	10± 2 min.	20± 2 min.	30± 5 min.	60± 25 min.	90± 25 min.	2-4 hour	24± 1 hour	48± 1 hour
¹¹¹ In-XYIMSR-01 Administration		X									
Blood & Plasma Collection	X		X	X	X	X	X	X		X	
¹¹¹ In-XYIMSR-01 SPECT/CT Imaging									X	X	X

5. CRITERIA FOR DISCONTINUATION: CANCELLATION/WITHDRAWL PROCEDURES AND EARLY STOPPING RULES.

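### Does the plan need a rule for lesions and organs outside the SPECT fields, given three fields of view in 3 patients and two in 7?

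*Combined protocol and SAP*

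**What the plan says.** Section 4 (Study Procedures, footnote 7) sets the coverage: "For the first three enrolled patients, a total of three fields of view will be acquired". Section 7.2 repeats it and adds that "for the remaining 7 patients two fields of view will be acquired". Neither place gives a body region, axial length, landmark or placement rule.

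Section 7.2 uses these scans for two purposes.

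- **Dosimetry.** The SPECT/CT "images will be used to perform the biodistribution and radiation dosimetry calculations". Time-activity curves "will be drawn for the whole body and the following organs: brain, breast, gallbladder" and a further list that ends with the gonads. Residence times are then found organ by organ. On the CT component: "The first time point acquisition for each field of view will include a high resolution CT".
- **Lesion comparison.** This is introduced "As an initial assessment of the diagnostic performance of" the new test. Three counts are planned, with descriptive statistics only: lesions seen on all modalities, lesions seen on "SPECT/CT but not with conventional imaging", and "the number of lesions detected with conventional imaging but not by" the SPECT/CT.

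Section 2.2 lists concordance with conventional imaging as a secondary objective. Section 3.2 requires 2 to 10 sites of at least 1.5 cm on CT or MRI of the chest, abdomen and pelvis. The calendar in Section 4 schedules a review of standard-of-care conventional imaging at screening and follow-up, with no anatomical limit.

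**The concern.** Seven of the ten patients have one field fewer than the first three. Unless the third field only repeats anatomy, less of their body is imaged. The lesion comparison has no not-imaged category and no restriction to anatomy that both tests covered. Applied word for word, a CT/MRI lesion outside the SPECT fields joins the conventional-only count, although it says nothing about the tracer. A SPECT finding outside the conventional scan range would join the SPECT-only count in the same way.

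The dosimetry text raises a parallel doubt. A brain curve is listed, while the imaging required at entry stops at chest, abdomen and pelvis. If a field includes the head, a finding there may have no conventional scan to set against it. If no field does, the brain curve cannot be drawn. A whole-body curve would also cover different anatomy in the two groups.

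At stake would be a first impression of tracer performance that looks worse than it is, and whole-body figures that are not like for like.

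**Working it through.** **Plan's own figure.** The plan gives no number on coverage. Its only sample-size figure is the safety statement in Section 7.1: zero events in 10 patients, 90% confidence, upper limit 25%. The exact two-sided 90% upper limit is 1 − 0.05^(1/10) = 25.9%, so the statement reproduces to within 0.9 points. It does not depend on coverage.

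**Inputs from the documents.** 3 patients with three fields; 7 with two; 2 to 10 entry-size sites per patient.

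**Inputs that must be assumed.** q is the share of the two-field patients' CT/MRI lesions that lie outside their fields. s is the share of in-field lesions seen on SPECT/CT. The documents give neither. No lesion is taken to be out of field in the first three patients.

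**Step 1: share of lesions in the two-field patients (w).** With equal lesions per patient, w = 7/10 = 0.70. The seven carry 14 to 70 entry-size sites and the first three carry 6 to 30. The extremes are therefore 14/(14 + 30) = 0.32 and 70/(70 + 6) = 0.92.

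**Step 2: lesions misplaced under the literal reading.** m = w × q.

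| q | w = 0.32 | w = 0.70 | w = 0.92 |
|---|---|---|---|
| 0 | 0% | 0% | 0% |
| 10% | 3.2% | 7.0% | 9.2% |
| 20% | 6.4% | 14.0% | 18.4% |

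At q = 10% this is 1.4 to 7 entry-size lesions among the 14 to 70.

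**Step 3: unscanned share of the conventional-only count.** The share is m / [m + (1 − s)(1 − m)].

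- q = 10%, w = 0.70: 0.07/0.163 = 43% at s = 90%; 0.07/0.349 = 20% at s = 70%.
- q = 20%, w = 0.70: 0.14/0.226 = 62% at s = 90%; 0.14/0.398 = 35% at s = 70%.
- q = 10% at the extremes of w: about 10% (w = 0.32, s = 70%) to 50% (w = 0.92, s = 90%).
- q = 0: 0% throughout.

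The count would thus be sensitive to q if two conditions held: q is above zero, and out-of-field lesions are scored as missed.

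**Step 4: do the documents support either condition?**

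- *Is q above zero?* Field length and placement are not given. If two fields span chest, abdomen and pelvis, no lesion found on the entry imaging is unscanned. Nothing in the text shows that they do not.
- *Would such a lesion be scored as missed?* The plan is silent. It says that findings on the two tests are compared, which can equally be read as covering only anatomy that both tests imaged.
- *Does the brain entry show that the ranges differ?* No. An organ list does not show that a field reaches the head. Section 3.2 sets a minimum for entry, not the comparator; the conventional imaging review in Section 4 has no anatomical limit.

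**Step 5: dosimetry.** Residence times are calculated for individual organs. An organ outside the images has no data to fit, so it yields no estimate rather than a wrong one. The plan defines no ten-patient mean whole-body curve, so mixed coverage does not bias any stated output.

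**The case for a change.** The best case for a change is that the three lesion counts are the whole analysis of a stated secondary objective. No model or test follows, so how a lesion is classified determines the result. The literal wording puts an unscanned lesion among the SPECT misses, and without a written rule the choice would be made after the images are seen. Attaching a CT to each field also fits distinct regions better than repeats, so the coverage gap is probably real. Naming the fields and adding a not-imaged line would cost a few words and no scans.

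Part of this stands. The anatomy is unnamed, the rule is unwritten, and the conventional-only count would be sensitive if q were above zero. But the worry about a choice made after seeing the images has little force here. Whether a lesion was inside a field is a matter of geometry, settled by the CT acquired with that field and not by tracer uptake. It can be checked later by anyone who holds the images. Low cost alone does not make a change necessary when a wrong result has not been shown.

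**Conclusion.** No change is needed. The plan leaves a detail unwritten that imaging analysts fill sensibly: a lesion that SPECT did not scan cannot be read as positive or negative, and an organ that was not imaged produces no curve. A wrong result needs both an out-of-field lesion and a reader who scores it as a tracer miss. The documents establish neither.

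The size is undetermined and may be zero. At an assumed q of 10%, a literal count would misplace 7% of CT/MRI lesions with equal lesions per patient, and about 3% to 9% across the splits that 2 to 10 sites per patient allow. These figures assume full coverage in the first three patients and apply the entry-size limits to all lesions.

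Only secondary, descriptive summaries in a 10-patient phase I study are involved. The safety objective, the halting rule and the sample size do not depend on coverage. The judgement would change if the fields were shown to leave out part of the chest, abdomen or pelvis and lesions there were then reported as missed by the tracer.
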